was rural households in the K-N District that used biofuels (wood, animal waste, and crop residue) as their main cooking fuel source, and that contained women and young children (demographic groups typically in closest proximity to cooking activities). Data from the HDSS enabled a cluster random selection of households from the district population that met the REACCTING eligibility criteria. The social structure in this region is such that groups of related households live in connected compounds. For the purposes of the HDSS, compounds are grouped into geographic **clusters**, with up to 99 compounds per cluster. These clusters are grouped into five geographic regions: four of these are primarily rural (North, East, South, and West), while the Central region contains Navrongo town and surrounding areas. For the REACCTING sample, we first eliminated households from the Central region, and then we randomly selected 25 clusters using population weighting to determine the number of clusters selected per region. Within each cluster, eight households were randomly selected from the population of households that met the study eligibility criteria, resulting in a total sample of 200 households.

[figure not shown]
The stove intervention of the REACCTING study includes four different intervention arms: Group A received two Gyapa stoves, Group B received two Philips stoves, Group C received one of each type of

stove, and Group D serves as the control for the duration of the study, but will receive their choice of stove at the conclusion of the study (the timing of which will coincide with the beginning of the research project described here). Stove stacking (i.e., households using new cookstoves alongside traditional cooking methods) had been observed in prior studies and we had earlier observed multiple stove use by the households in the study area. Multiple stoves were provided to each intervention household to increase the probability that households would begin to substitute away from traditional stoves rather than simply adding a new stove to their cooking technology mix. Randomization into intervention groups was done at the cluster level: i.e., within each of the 25 clusters, there are 2 households in each of the 4 REACCTING intervention groups.

REACCTING Preliminary Results

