The design of our intervention requires that we offer stoves that are similar to those offered for the REACCTING study, since we are measuring whether exposure to these technologies through peers influences adoption decisions. However, our experience in the REACCTING study revealed some key challenges with both the Gyapa and Philips stove models, such that we have elected to use slightly different stove models for this project. Through initial lab testing at CU as well as consultation with individuals in the study area, we have selected the Greenway Jumbo stove as a rocket-type stove, similar to the Gyapa, and the ACE1 stove as a forced-draft stove, similar to the Philips.

Peer Effects

Random variation in exposure to peers with cookstove experience will be accomplished through selection of S Group households that vary in terms of their proximity and social contacts with the R Group. The **S1** subgroup will be drawn from the same clusters as the R Group households (25 R Group clusters). S1 group households will thus be located in close physical proximity to R Group households with new stove experience, and are expected to have several social ties to these households. Meanwhile, the **S2** subgroup will consist of 25 clusters randomly selected from the area of the K-N Districts outside of a certain buffer distance from the R Group clusters. Data from the REACCTING study and additional pretesting will be used to select a buffer distance that minimizes the expected number of ties between R and S2 Group households; given that there are more than 300 clusters in the district and only 25 were included in the R Group, these ties are expected to be minimal (and will be measured as part of our data collection). Because the R Group clusters were randomly selected initially, and the S2 clusters will also be randomly selected, the study design ensures that in expectation the only differences between S1 and S2 group households is the former's higher level of exposure to peers with cookstove experience, enabling us to test the impacts of this exposure on our outcomes of interest (perceptions and technology adoption and use).

Prices

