S1 group households will be selected using GIS data to identify the *nearest neighbors*, meeting the above eligibility criteria, of each of the 6 REACCTING households that received stoves in that cluster during the REACCTING intervention phase. In the non-peer clusters, 6 seed households meeting the above eligibility criteria will be randomly selected, and then S2 group households will be selected as the nearest neighbors of those seed households. This procedure is used to create as similar as possible selection criteria and sampling methods between the peer (S1) and non-peer (S2) groups.

Component #2: P3 Gas

This component of the study involves two subject populations: LPG suppliers, and urban households. For the supply survey, all LPG refilling stations in the Upper East Region, and all retail shops selling LPG stoves or cylinders in the K-N Districts, will be eligible for inclusion in the study (16 businesses in total).

For the urban households, we will use the same demographic inclusion criterion as in the rural sample (at least one woman in household aged 18-55 and one child under five). As in the rural areas, we will first randomly select clusters from the urban area, and then randomly select households within each cluster, for a total of 300 households in this component. These subjects will complete an initial baseline survey (Activity 1.2) and will then be enrolled in the intervention (Activity 2.1) and follow up data collection. In the urban area, the majority of respondents belong to the Kasem ethnic group. As above, the primary cook is the primary participant, and if another individual in the household is responsible for making financial decisions for the household, this individual will also complete household surveys and will be present when stove offers are made.

VII. VULNERABLE POPULATIONS

> Not applicable.

VIII. RECRUITMENT METHODS

P3 Bio and P3 Gas Household Recruitment

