Survey Data	Household-level social network, perception, behavioral, health,	ArcGIS, CSV, DTA (Stata)	Units, lat/lon of compounds/ houses	Team access only to full dataset with identifiers / De- identified data open access with	Non- commercial use only	CU password protected computer

	demographic, and socioeconomic data			registration / statement of interest		
Stove Use Data	Time series measurements of stove temperature	ASCII, CSV, EXCEL, MAT (Matlab)	Units, variables (compounds, stove type) methods, uncertainty	Open access with registration/ statement of interest	Non- commercial Use Only	CU password protected computer and servers
Personal Exposure, Proximity, and Air Quality Data	48 hr real-time personal CO data; 48-hr integrated personal PM _{2.5} samples; time series of individual proximity to stoves/sources; household environment CO, CO ₂ , and PM _{2.5} samples (NO and VOCs in subgroup)	CSV, TXT, EXCEL, MAT, (Matlab)	Units, variables, (Lat/lon of measurements, characteristics) methods, uncertainty and calibrations	Team access only to full dataset with identifiers / De- identified data open access with registration / statement of interest	Non- commercial use only	CU password protected computer and servers
Short Term Stove Use and Proximity Data	48 hours of 30- second-interval photographs	JPG	Timestamp, Date, Temperature	Team access only to full dataset with identifiers/ De- identified data open access with registration / statement of interest	Non- commercial use only	CU password protected computer and servers

Types of data

The raw data generated by the proposed research includes (a) quantitative social survey data and analyses; (b) time series measurements of stove temperature from the Stove Use Monitors (SUMs), and (c) personal exposure, proximity to stoves, and microenvironmental (near-stove) air quality data. Surveys will be conducted using paper hard copies generated using the Remark Office OMR software, a "scantron" like format that allows responses on subsequent .pdf files to be read in to Excel files automatically. Air quality data will be collected from the instruments in the field in the form of raw sensor signals, typically voltages, with time stamps. In addition to this field data, we will also be routinely compiling calibration data for each sensor. This calibration data will be in the same format as the field data.

Data Storage and Archival

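### Some S1 households may already have access to a recipient's improved stoves, so an S1-S2 purchase gap cannot be put down to learning about quality alone

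*Combined protocol and SAP*

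**What the plan says.** All references are to the combined protocol and SAP.

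- **Selection of S1 (Section VI, Inclusion / Exclusion Criteria).** S1 households are the GIS-nearest eligible neighbours "of each of the 6 REACCTING households that received stoves in that cluster during the REACCTING intervention phase".
- **Selection of S2 (same place).** Six eligible seed households per cluster are drawn at random, and "S2 group households will be selected as the nearest neighbors of those seed households". The stated aim is to make the two sampling procedures as alike as possible.
- **Eligibility (same place).** The criteria are rural classification, biofuel as main fuel, a woman aged 18-55 and a child under five. None concerns compound membership or existing improved stoves. The fuel criterion does not screen out users of the earlier stoves, because those burn wood.
- **Setting (Section III, REACCTING Study Sample and Intervention Design).** In this area "groups of related households live in connected compounds". "Multiple stoves were provided to each intervention household": two Gyapa, two Philips, or one of each.
- **Stoves offered (Section IV, Stove Selection).** The new models are chosen to be similar in type to the earlier ones.
- **Identification (Section IV, Peer Effects).** The only expected difference between the groups is said to be S1's "higher level of exposure to peers with cookstove experience".
- **Mechanism.** Research question 2 (Section I) asks how peers' histories help potential users learn about product quality. The conceptual model in Section II has peers act through perceived value.

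The plan does not mention sharing or borrowing of earlier-study stoves, and it specifies no analysis to separate that from learning.

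**The concern.** The S2 procedure copies the sampling geometry of S1 but not the presence of stoves. A household next to a recipient, possibly a relative in the same compound, may be able to cook on or borrow one of two improved stoves. If so, it has less need to buy a similar one, whatever it believes about quality.

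This matters because mechanism is the purpose of the study. Section II observes that earlier studies read negative peer effects as downward-revised expectations without measuring expectations. Background access would push purchase in the same direction as the negative peer effect in Table 1.

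It could also imitate the planned price-by-peer interaction. A substitute in the compound should matter little when a stove is free and more when it must be paid for. Table 1 assumes that pattern: full uptake at P0 in both groups, and a larger fall in S1 at P2. In use analyses, some S1 households might also start with improved-stove use that S2 lacks.

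**Working it through.** **1. How many S1 households could share a compound with a recipient?** The plan does not say. Section III gives about 30,000 households and up to 99 compounds per cluster; Section IV gives more than 300 clusters.

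- At the maximum of 99: 300 x 99 = 29,700 compounds, and 30,000 / 29,700 is about 1 household per compound.
- At an assumed 50: 300 x 50 = 15,000 compounds, or 2 households per compound.

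A compound-mate must also meet the eligibility criteria. The share is unknown and could be small.

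**2. Table 1's peer row on adoption.** Inputs: 75% in S2, 60% in S1, N = 147 each, stated power 0.838. Alpha and sidedness are not stated. I used a two-proportion normal approximation with pooled null variance, one-sided alpha 0.05 and a continuity correction of 1/147 = 0.0068:

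- null standard error = sqrt(2 x 0.675 x 0.325 / 147) = 0.0546
- alternative standard error = sqrt((0.75 x 0.25 + 0.60 x 0.40) / 147) = 0.0539
- z = (0.15 - 0.0068 - 1.645 x 0.0546) / 0.0539 = 0.99, so power = 0.839

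This reproduces the stated figure, with no allowance for clustering. Two-sided without correction gives 0.787. The point does not depend on which was intended.

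**3. Gap from access alone.** Assume no learning effect, 75% purchase without access, a share f of S1 with access, and a proportional cut r in purchase among them. Then gap = 0.75 x f x r. Both f and r are assumptions.

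| f | r | S1 purchase | Gap (points) | P(reject), one-sided corrected | P(reject), two-sided uncorrected |
|---|---|---|---|---|---|
| 5% | 50% | 73.1% | 1.9 | 0.08 | 0.06 |
| 10% | 50% | 71.25% | 3.75 | 0.15 | 0.11 |
| 20% | 50% | 67.5% | 7.5 | 0.36 | 0.29 |
| 40% | 50% | 60% | 15 | 0.84 | 0.79 |
| 20% | 100% | 60% | 15 | 0.84 | 0.79 |

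The effect runs from negligible to the whole planned gap of 75 - 60 = 15 points.

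**4. Interaction row.** Table 1 assumes a 60% fall at P2 in S1 and a 40% fall in S2, so purchase is 40% against 60%, a 20-point gap. With access alone, 0.60 x f x r = 0.20 requires f x r = 0.33, for example f = 67% with r = 50%. Smaller values would reproduce part of the gap.

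**5. Precision without same-compound households.** If 20% were lost from each group, n = 147 x 0.8 = 117.6. With the formula in step 2, z = (0.15 - 0.0085 - 1.645 x 0.0611) / 0.0603 = 0.68, and power for a true 15-point effect falls from 0.838 to about 0.75.

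**The case against.** The strongest reply is that access through a neighbour's stove is part of the exposure. Section IV makes physical proximity and social ties to recipients the treatment, and access arises only because the peer has a stove. That stands. A reader might infer that the S1-S2 gap is spurious or the design invalid. The documents do not support this: the contrast still estimates the total effect of living near recipients, and only its reading as learning is open.

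A reader might also infer that S1 households will often be in the recipient's own compound, at zero recorded distance. Nothing supports often; the counts above allow as few as about one household per compound. Table 6 lists "lat/lon of compounds/ houses" as metadata for the survey data. It does not say at which level the coordinates used for selection were held.

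The plan also has some leverage on mechanism. Perceptions are measured before and after adoption, and Table 1 has a separate peer row for perceived quality. If access lowered purchase without changing beliefs, an adoption gap would appear without a perception gap. Baseline stove types and social networks are collected too (Section XII). This helps, but no analysis is specified that uses these data for the purpose, and the survey is not said to ask about using another household's stove.

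Finally, two stoves may not exceed a recipient's own needs, and trying a relative's stove may raise demand. Section II allows a peer effect of either sign. So the direction is uncertain, which is itself a reason to look at the two routes separately.

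**Conclusion.** The point holds as a limit on interpretation. The selection rule and eligibility criteria allow some S1 households to have access to a close substitute that S2 lacks, so neither a purchase gap nor a larger price response in S1 can be attributed to learning about quality alone. The full contrast stays valid as a total effect of proximity.

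The share affected, the size and the direction cannot be determined from the documents. The figures of 1.9 to 15 points rest on assumed values of f and r and show only that the effect could be trivial or as large as the planned gap. No number in Table 1 is shown to be wrong by this.

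It might be inferred that the selection rule must change, or that the contrast without same-compound households should become the main peer result. The documents do not justify that. It would remove the closest social ties, reduce power and still not prevent borrowing between adjacent compounds. A prespecified sensitivity analysis is a proportionate improvement.

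**What to change.** 1. Keep the selection rule, and keep the full S1-S2 contrast as the main peer analysis, described as the total effect of living near recipients.
2. From the surveillance compound identifiers, flag each household that shares a compound with its index recipient (S1) or its seed (S2), and report the counts.
3. Prespecify a sensitivity analysis of the adoption, use and price-by-peer contrasts that leaves out flagged households in both groups. Compound membership is a basis that can be applied alike in both groups, whereas prior stove use may itself result from the exposure.
4. From the baseline stove-type data, report how many S1 and S2 households were using an earlier-study stove before the offer. Note that this may miss use of a stove belonging to another household.
5. Describe an adoption gap as learning only if it persists in the sensitivity analysis and is accompanied by a gap in perceived quality.

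The cost is one flag and some extra analysis, largely from data already held or planned. The sensitivity contrast will be less precise (power about 0.75 against 0.838 if 20% of each group were dropped, before any allowance for clustering) and it omits the closest ties. It should therefore be read beside the main contrast and not in place of it.

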Using the cluster-randomized assignment of selected households to different price treatments along with prior random selection of the REACCTING study clusters (and subsequent inclusion of non-REACCTING households), we will estimate a variety of reduced-form and potentially structural models using the exogenous variables of stove price, as well as cluster-level prior adoption and usage. These models will be used to investigate the validity of the broad conceptual model, to test specific research hypotheses emerging from the formal economic model in Section 4.1, and to explore additional research questions, including the relationship between perceived stove quality and instrument-based measures of personal exposure to emissions.

The study's power to detect significant effects will vary depending on the specific outcome variable used (e.g., easier to detect effects for continuous vs binary variables), the cell sizes (smaller for interactions than for main effects), and the effect sizes, which are always difficult to estimate *a priori*. Table 1 shows power estimates for a sample of possible analyses under different assumptions.

Effect	Outcome variable	Assumed effect size across	Power to
		groups being compared	detect
Main effect of price	Purchase / receipt of any stove by	100% in P0 (N=70) vs 75% in	0.999
on adoption	household (binary)	P1 (N=84)	
		100% in P0 (N=70) vs 50% in	0.999
		P2 (N=140)	
Main effect of price	Reported use of stove on day prior to	50% in P0 (N= 70) vs 75% in	0.965
on stove use	survey (binary)	P2 (N=140)	
		(positive price effect)	

Table 1: Power to detect sample of possible treatment effects under different assumptions

Main effect of price on perceived quality	Continuous stove quality index (0 to 100) from Likert-scale questions (Assuming normal dist. with std. dev. of 25 pts)	75 pts in P1 (N=84) vs 65 pts in P0 (N=70) (positive price effect)	0.800
Main effect of peers on adoption	Purchase / receipt of any stove by household (binary)	75% in S2 (N=147) vs 60% in S1 (N=147) (negative peer effect)	0.838
Main effect of peers on perceived quality	Continuous stove quality index (0 to 100) from Likert-scale questions (Assuming normal dist. with std. dev. of 25 pts)	50 pts in S1 (N=147) vs 60 pts in S2 (N=147) (negative peer effect)	0.96

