Instrument-based measurements												
Data analysis												
Dissemination												
- Preparation of reports and peer-												
reviewed publications												
- Presentation at scientific												
conferences												
- Workshop in study area												

V. FUNDING

This research is being funded by the National Science Foundation's Economics program and the National Institutes of Health's Clean Cooking Implementation Science Network.

VI. ABOUT THE SUBJECTS

Component #1: P3 Bio

As shown in Figure 5, a total of 300 households will be enrolled in the P3 Bio component of the study. In each household, the primary cook (typically female, aged 18-55 years old) will serve as the main study participant. In households where another male household member makes financial decisions, we will conduct a secondary survey with this individual as well. We anticipate that all of these households will complete the study. The study population includes two main ethnic groups: Kasem and Nankam. The population will be split roughly evenly between these two groups.

Table 3: Subject Populations

Subject Population(s)	Number to be enrolled in each group
Group S1: Rural households from the same	150 households
clusters as REACCTING study households	

Group S2: Rural households from different150 householdsclusters from REACCTING study households150 households

Inclusion / Exclusion Criteria

Sample selection will proceed in two phases. First, clusters will be selected for inclusion in the study. All of the 25 REACCTING study clusters will be included to form the S1 group clusters. GIS mapping will then be used to *exclude* clusters that are close to those S1 clusters (using a buffer distance determined using preliminary data on social ties), and 25 S2 group clusters will then be randomly selected from the remaining clusters.

Second, the required number of households will be selected from each cluster. We will use the same inclusion and exclusion criteria used to select households in the existing REACCTING study. Using data from the district's demographic surveillance survey, a sample frame of eligible households will be created using the following inclusion criteria:

- Classified as "rural"
- Uses biofuel as main cooking fuel source
- Has woman in household aged 18-55 and at least one child under five (since women and children are the most vulnerable to cookstove smoke)

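### Cluster-level stove usage is called exogenous, but within S1 only the index neighbour's REACCTING arm is randomised, and no planned analysis uses it

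*Combined protocol and SAP*

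**What the plan says.** All places are in the combined protocol and SAP.

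- **Peer contrast.** Section IV, Peer Effects, rests on S1 v S2 and holds that "in expectation the only differences between S1 and S2 group households is the former's higher level of exposure to peers with cookstove experience". The peer rows of Table 1 use the same two groups.
- **Exposure variable.** Section IV, Analysis of Key Research Questions and Power Calculations, describes reduced-form and possibly structural models "using the exogenous variables of stove price, as well as cluster-level prior adoption and usage".
- **Earlier allocation.** Section III, REACCTING Study Sample and Intervention Design, states that "within each of the 25 clusters, there are 2 households in each of the 4 REACCTING intervention groups". Group A had two Gyapa stoves, B two Philips and C one of each. D was the control and gets its chosen stove as the present study starts.
- **S1 sampling.** Section VI, Inclusion / Exclusion Criteria, states that "All of the 25 REACCTING study clusters will be included to form the S1 group clusters". The households are then the nearest eligible neighbours "of each of the 6 REACCTING households that received stoves in that cluster during the REACCTING intervention phase". Table 3 gives 150 S1 households.
- **Price.** Section IV, Prices, sets one price per cluster.
- **Replacements.** Section VIII replaces households that refuse or cannot be found from a randomly drawn list for the cluster.

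No section uses the index household's arm or a comparison within clusters.

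**The concern.** A cluster-level exposure measure can separate S1 from S2, because the REACCTING clusters were chosen at random. Within S1 it carries no randomised information. Each cluster got the same number and mix of stoves, so one cluster can show more usage than another only through what its households did with them. The factors behind that (fuel supply, income, cooking habits, local leadership) may also drive demand for the new stoves. A coefficient on usage among S1 clusters is then open to ordinary confounding, although the plan calls the variable exogenous.

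Meanwhile the design does hold randomised variation in peers' experience, one level down: whether the recipient next door had rocket stoves, forced-draft stoves or one of each. Averaging to the cluster removes it. Research question 2 asks how peers' histories teach about quality, households choose between a rocket and a forced-draft model, and stove type is a listed adoption measure. Section III also reports that Groups A and C cut three-stone use more than Group B, so the arms did give peers different experiences.

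**Working it through.** **1. Does assigned exposure vary between S1 clusters?** With 2 households per arm in each cluster, every S1 cluster has 2 A + 2 B + 2 C = 6 recipients. The assigned mix is constant, so remaining differences in usage are not assigned.

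**2. Does it vary within clusters?** S1 has 150/25 = 6 households per cluster, against 6 recipients. That implies one neighbour per recipient; this is derived, as the plan gives no number per recipient. Expected count per arm: 25 × 2 = 50. Among the six recipients the A/B/C labels can be permuted in 6!/(2!·2!·2!) = 90 ways per cluster, which is the basis for a permutation test. Price and location effects common to the cluster cancel.

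**3. Table 1's peer row for perceived quality** (10 points, SD 25, 147 v 147, stated power 0.96). SE = 25·√(2/147) = 2.92 and 10/2.92 = 3.43.
- One-sided 5%: Φ(3.43 − 1.645) = 0.963, which matches.
- Two-sided 5%: Φ(3.43 − 1.96) = 0.929.

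The stated figure therefore fits a one-sided test with no allowance for clustering. The plan states neither, so this is inferred from the match. Two-sided tests are used below.

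**4. Precision of the index-arm contrast.** With cluster fixed effects, SE = 25·√[(1 − ICC)(1/n₁ + 1/n₂)] and power = Φ(δ/SE − 1.96). The documents give no ICC, so a range is assumed.

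| Contrast | ICC | SE | Power, δ = 10 | Power, δ = 5 |
|---|---|---|---|---|
| A v B (50 v 50) | 0 | 5.00 | 0.52 | 0.17 |
| | 0.05 | 4.87 | 0.54 | 0.18 |
| | 0.2 | 4.47 | 0.61 | 0.20 |
| B+C v A (100 v 50) | 0 | 4.33 | 0.64 | 0.21 |
| | 0.05 | 4.22 | 0.66 | 0.22 |
| | 0.2 | 3.87 | 0.73 | 0.25 |

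The 10 points are borrowed from Table 1's S1 v S2 row, an exposed v unexposed effect. The 5 points illustrate dilution by half.

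**5. Detectable differences, A v B, 80% power.** (1.96 + 0.84) × SE gives about 14.0 points at ICC 0 and 12.5 at ICC 0.2. For a binary outcome at ICC 0, the difference is about 25 percentage points upward from 60%, or 27 downward from 75%.

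**6. Against S1 v S2.** Effective size per group is 150/(1 + 5·ICC) for S1 v S2 and 50/(1 − ICC) for A v B. They meet at ICC 0.25, where 150/2.25 = 50/0.75 = 66.7. Below that S1 v S2 is more precise: its power for 10 points is 0.93 at ICC 0 and 0.69 at ICC 0.2.

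**The case against.** The strongest reply is that nothing planned depends on this regression. The model wording is open-ended and does not exclude it, and social ties are to be measured. That is fair, and the plan should not be read as forbidding the analysis. But permission is not pre-specification. No section requires the index link to be kept, and the reply leaves untouched the description of usage within S1 as exogenous.

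Several limits stand:

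- **Different question.** All three index arms are exposed, and neighbours of Group D are not sampled. A reader might infer that this contrast is cleaner than S1 v S2 and could replace it. The documents do not support that: the exposed v unexposed question in research questions 2 and 3 still needs S2.
- **Cross-exposure.** A neighbour of an A household shares its cluster with four Philips owners (2 B + 2 C). Group D's stoves arrive as the study begins, and all participants see both models demonstrated. The contrast is diluted, and the borrowed 10 points may be far too large.
- **Replacements.** A replacement from the cluster list need not neighbour any recipient. Nor is it said what happens when one household is nearest to two recipients. An exact 50/50/50 split cannot be claimed.
- **Different stoves.** S1 is offered Greenway and ACE1, which are similar to Gyapa and Philips but not the same.
- **Use among purchasers.** Purchase may depend on index arm. At Table 1's 60% adoption, about 0.6 × 50 = 30 per arm would remain, no longer a randomised comparison.

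Section III's remark that REACCTING was randomised at the cluster level might be read as contradicting all this. Its own explanation describes balance within each cluster, so it is a wording matter only.

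**Conclusion.** The point holds in a limited form. Usage differences among S1 clusters are not randomised and should not be called exogenous. The index household's arm is randomised within cluster, at a fixed price, and goes unused. The size is modest: about 50 households per arm before replacements, power of 0.52 to 0.73 across the two contrasts for a 10-point effect, and about 0.2 if dilution halves it. That supports a pre-specified secondary analysis and no more. It does not show that S1 v S2 is invalid or that any planned estimate of the price effect is biased. The figures rest on Table 1's SD of 25, an assumed ICC of 0 to 0.2, one neighbour per recipient, and random assignment of REACCTING arms among the households of each cluster.

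**What to change.** 1. Record for every S1 household its index REACCTING household, that household's arm, and whether the S1 household is a replacement.
2. Set in advance how to treat replacements (exclude those without an index household, or assign them by a stated rule) and households nearest to two recipients.
3. Pre-specify a secondary analysis of S1: stove type chosen and perceived quality of each type, regressed on index arm (A, B, C) with cluster fixed effects, and p-values from permuting arms within cluster. Name one contrast and outcome as leading, because several arms, types and outcomes are involved.
4. If use is analysed, include all S1 households and count non-purchasers as no use of a new stove.
5. Drop the description of cluster usage within S1 as exogenous; report any such model as observational.
6. State the limits: types of exposure rather than exposure v none, dilution within clusters, similar but not identical models, low power.
7. Reword the REACCTING description to say arms were randomised within clusters.

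The cost is three linking variables, one extra set of regressions and a few sentences. No new households or visits are needed.
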